5.5.6 Medication for Opioid Use Disorder Treatment History

The MOUD treatment history data will be listed.

5.5.7 Urine Drug Screen Results

For each visit, data from the urine drug screen (UDS) results will be assessed to derive the number and percentage of subjects with positive opioid use, using observed data.

For this analysis, opioids will include the results for opioids, methadone, fentanyl, oxycodone, and morphine. If the result for any of these are positive, the subject will be considered positive for opioids.

The usage of individual substances collected via the UDS will be listed.

5.6 Interim Analyses

No formal interim analyses are planned for this study.

6 SUPPORTING DOCUMENTATION

6.1 Appendix 1 List of Abbreviations

Table 5 List of Abbreviations

Abbreviation	Term
AE	adverse event
AESI	adverse event of special interest
ALT	alkaline aminotransferase
BMI	body mass index
CRF/eCRF	case report form/electronic case report form
CSR	clinical study report
ECG	electrocardiogram
EOT	end-of-treatment
ET	early termination
ICF	informed consent form
INDV	Indivior

Abbreviation	Term
MedDRA	Medical Dictionary for Regulatory Activities
MOUD	medication for opioid use disorder
OUD	opioid use disorder
PT	preferred term
SAE	serious adverse event
SAP	statistical analysis plan
SC	subcutaneous
SD	standard deviation
SOC	System Organ Class
TEAE	treatment-emergent adverse event
TLF	tables, listings and figures
UDS	urine drug screen
ULN	upper limit of normal
USPI	United States Prescribing Information

6.2 Appendix 2: Changes to Protocol-Planned Analyses

The definitions of completion of the treatment period versus completing treatment were clarified.

The MOUD treatment history data will be listed only and not summarized.

The reporting of AEs was specified as a listing only and no summary tables in the case of \leq 6 AEs.

6.3 Appendix 3: Definition and Use of Visits and Visit Windows in Reporting

Nominal visits will be used for the analysis without regard to visit windows. The nominal visits will be labelled in TLFs as Injection 1 – Injection 5 and ET/EOT.

Unscheduled visits will be given an analysis visit number in sequential order according to chronological date/time following the most recent scheduled visit.

6.4 Appendix 4: Definition of Protocol Deviations

A protocol deviation is any change, divergence, or departure from the study design or procedures defined in the protocol. Important protocol deviations are a subset of protocol deviations that may significantly impact the completeness, accuracy and/or reliability of the study data or that may significantly impact a subject's rights, safety, or wellbeing.

The important deviations will not be considered in the statistical analyses or in the definitions of analysis populations. All deviations will be listed.

6.5 Appendix 5: Methods to Manage Missing Data

Observed data is used for analysis, unless handling of missing data is described otherwise within the analysis description or in the sections below.

6.5.1 Missing Date Information for Adverse Events

If the AE start date is missing, and the AE stop date is on or after the first dose of study medication, then the AE start date will be imputed as the date of the first dose of study medication.

If the AE start date is missing, and the AE stop date is not missing and before the first dose of study medication, then the AE start date will be imputed as the stop date.

Partial AE Start Date

Missing day and month

- If the year is the same as the year of the date of the first dose of study medication, then the day and month of the date of the first dose of study medication will be assigned to the missing fields.
- If the year is before the year of the date of the first dose of study medication, then December 31 will be assigned to the missing fields.
- If the year is after the year of the date of the first dose of study medication, then January 1 will be assigned to the missing fields.

Missing month only

• The day will be treated as missing and both month and day will be replaced according to the above procedure.

Missing day only

- If the month and year are the same as the month and year of the date of the first dose of study medication, then the day of the first dose of study medication will be assigned to the missing day.
- If either the year is before the year of the date of the first dose of study medication or if both years are the same but the month is before the month of the date of the first dose of study medication, then the last day of the month will be assigned to the missing day.
- If either the year is after the year of the date of the first dose of study medication or if both years are the same but the month is after the month of the date of the first dose of study medication, then the first day of the month will be assigned to the missing day.

If the imputed AE start date is after the AE stop date, then the imputed AE start date will be set to the AE stop date.

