## **10.2** Assessing and Documenting Adverse Events

The Investigator is ultimately responsible for assessing and reporting all AEs as outlined in the protocol. The assessment and reporting of AEs may be delegated to a medically qualified sub-Investigator, trained on this study protocol, who is listed on the delegation of authority log. All AEs regardless of suspected causal relationship to the study drug will be reported as described in this protocol.

Adverse events should be volunteered by the subject or solicited from the subject using a standard statement, obtained from examination of the subject at a clinic visit, or from observations of clinically significant laboratory values or special examination abnormal values.

All AEs are to be assessed and recorded in a timely manner and followed to resolution or until the Investigator determines that there is not an anticipated resolution. Each AE is to be documented with reference to severity, date of occurrence, duration, treatment and outcome. Furthermore, each AE is to be classified as being serious or non-serious. In addition, the Investigator must assess whether the AE is study drug-related or not.

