# 10.3 Time Period for Collecting Adverse Events

Adverse events will be collected from the time of signed informed consent (including ongoing AEs at the INDV-6000-403 EOT) until completion of the EOT visit. Any subject with ongoing AEs at the INDV-6000-404 EOT will be followed up by telephone 4 weeks later for a safety follow up to assess the ongoing AEs.

Subjects with ongoing SAEs at the safety follow up telephone contact that, in the opinion of the Investigator, are associated with the study drug, will be followed and reported as described in Section 11. Subjects with ongoing AEs at safety follow up telephone contact that, in the opinion of the Investigator, are associated with the study drug, will be followed and reported as described in Section 10.2.

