5.3.1 Treatment Emergent Adverse Events – Definition of Endpoint

A TEAE is defined as an AE observed after starting, that is having a start date/time on or after the date/time of the first administration of SUBLOCADE in this study. Any AEs ongoing at the INDV-6000-403 EOT were to be recorded in this study; however, note that these are not TEAEs in this study per this definition.

If subject experiences an event both prior to starting administration of SUBLOCADE and ongoing during the treatment, the event will be considered a TEAE (of the treatment) only if it has worsened in severity (i.e., it is reported with the date of worsening as the new start date/time) after starting administration of SUBLOCADE in this study.

Adverse events will be coded using the MedDRA dictionary and grouped by primary system organ class. The Investigator determines the intensity of AEs and the relationship of AEs to study therapy.

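### Does SAP 6.5.1 need a further rule for adverse events with no start or stop date, or with no onset time?

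*SAP*

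**What the plan says.** SAP 5.3.1 defines a TEAE as an event "having a start date/time on or after the date/time of the first administration of SUBLOCADE in this study". Of AEs still ongoing at the end of the feeder study it says that "these are not TEAEs in this study per this definition", and its next paragraph readmits an event only if it worsens after dosing starts in this study.

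SAP 5.3 refers to SAP 6.5 for missing data. The default there is: "Observed data is used for analysis, unless handling of missing data is described otherwise". SAP 6.5.1 then sets these rules for AE start dates:

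- Start wholly missing, first rule: "If the AE start date is missing, and the AE stop date is on or after the first dose of study medication", the start becomes the first-dose date.
- Start wholly missing, second rule: "If the AE start date is missing, and the AE stop date is not missing and before the first dose of study medication", the start becomes the stop date.
- Start partly known: it becomes the first-dose date when the known part agrees with the first dose. Otherwise it becomes the end of the earlier period or the beginning of the later one.
- An imputed start may not fall after the stop date.

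On collection, Protocol 10.2 says: "Each AE is to be documented with reference to severity, date of occurrence, duration, treatment and outcome". Protocol 10.3 says: "Adverse events will be collected from the time of signed informed consent". It also says: "Any subject with ongoing AEs at the INDV-6000-404 EOT will be followed up by telephone 4 weeks later", so AEs without a stop date are foreseen.

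**The concern.** The primary endpoint is the proportion of subjects with a TEAE, so each AE must be classifiable. Three things appear to get in the way.

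1. **No dates at all.** Neither rule for a wholly missing start applies when the stop date is missing too. If the observed-data default is read as leaving the start blank, the event cannot be shown to meet SAP 5.3.1. The same event with a stop date after dosing would be counted. The events at risk would be the unresolved ones.
2. **No onset time.** SAP 5.3.1 compares date and time, while SAP 6.5.1 imputes dates only, and Protocol 10.2 names a date of occurrence but no time. AEs are collected from consent, and screening can share Day 1 with the first injection, so an event before the injection and one after it may carry the same date.
3. **Order of rules.** SAP 6.5.1 does not refer back to SAP 5.3.1. Applied alone, it would give some carried-over AEs the first-dose date and so make them look treatment-emergent.

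At stake would be one or more subjects wrongly counted or left out in a study of at most 25.

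**Working it through.** The plan states no figure on this point, so there is none to reproduce. The check runs the SAP 6.5.1 rules over patterns of missing dates and then applies SAP 5.3.1.

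| Start date | Stop date | Start under SAP 6.5.1 | Status by date, SAP 5.3.1 |
|---|---|---|---|
| wholly missing | on or after first dose | first-dose date | TEAE |
| wholly missing | before first dose | stop date | not a TEAE |
| wholly missing | missing | no rule | undetermined |
| only the year, same as first dose | missing | first-dose date | TEAE |
| month and year, same as first dose | missing | first-dose date | TEAE |
| month and year, earlier month | missing | last day of that month | not a TEAE |
| complete, equal to first-dose date, no time | missing | not imputed | TEAE on the date alone |

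**No dates.** The third row is a true omission. A wholly missing start with a stop date known only to the first-dose month is a near neighbour, because it cannot be compared with the first dose. The other rows follow one pattern: when the record does not place onset before the first dose, the AE is given the first-dose date and counted. An analyst who extends that pattern counts the undated new AE as well. The omission is also hard to reach. It needs an AE with not even a year of onset, although Protocol 10.2 requires a date of occurrence, Protocol 4.1 has AEs assessed at visits about every four weeks, and Protocol 13.2 has CRF omissions reviewed and queried.

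**No time.** When only dates can be compared, an AE dated on the first-dose date meets the date criterion in SAP 5.3.1. The imputations above rely on this, since they set that date and supply no time. The only AEs this could misplace are untimed ones that began on Day 1 before the injection. If onset is assumed uniform over Day 1 to Day 141, the share of AEs beginning on Day 1 is 1/141 = 0.7%. It would be higher if AEs cluster at injection, and only the part of it before the injection matters.

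**Carried-over AEs.** SAP 5.3.1 excludes them unless they worsen, and SAP 5.5.1 lists them separately as not treatment-emergent. What is missing is a cross-reference, not a rule.

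**How often dates are imputed.** Pair 365 first-dose dates with onset 0 to 140 days later: 365 × 141 = 51,465 pairs.

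- Onset in the same calendar month as the first dose: 5,738/51,465 = 11%. This is the share given the first-dose date when only the day is missing.
- Onset in the same calendar year: 41,595/51,465 = 81%. This is the share when only the year is known.

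The 81% assumes first doses spread evenly over a year. For a single first-dose date it is 78/141 = 55% on 15 October, 17/141 = 12% on 15 December and 141/141 = 100% on 1 January. These are rates of imputation, not of error: for a new AE that began after dosing, the imputed date gives the right TEAE status.

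**Effect of one subject.** A reclassified subject with no other TEAE moves the proportion by 1/N: 1/25 = 4.0 points at the planned maximum, and 1/20 = 5.0 or 1/15 = 6.7 points if fewer enrol (both smaller values of N are assumptions). Two such subjects at N = 25 move it by 2/25 = 8.0 points.

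**The case for a change.** The strongest case for a change is that the endpoint is primary and the repair is cheap. The second rule expressly requires a stop date that is present, so the authors had absent stop dates in mind and still wrote no branch for them. A programmer who follows the observed-data default literally could leave the start blank and drop the event. Protocol 9.4 takes the time of dose as the completion of the injection, whereas Protocol 14.4.1 counts from the start of administration, so an AE that begins during the first injection meets one definition and not the other. TEAE status can also matter when few AEs are reported: the summaries in SAP 5.3.2 need more than six AEs, but SAP 5.5.1 produces the table of AE occurrences from one AE upward.

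The literal omission stands, and so does the remark about the occurrences table. The rest is weaker.

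- The default does not say that an AE with an unknown start is not a TEAE; it leaves the status open. SAP 5.3.1 also begins from an AE observed after dosing has started, which a new AE first seen at a later visit satisfies.
- Protocol 10.2 is a general list and does not specify CRF fields. The CRF is not among the documents. Both Protocol 14.4.1 and SAP 5.3.1 have a worsened event reported with a new start date and time, which suggests that time is captured.
- The difference between the start and the completion of the injection affects only an AE beginning within a single subcutaneous injection. SAP 1 makes the SAP's definition the governing one.

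**Conclusion.** No change to the plan is needed. SAP 6.5.1 has no explicit branch for a new AE with both dates missing and does not mention a missing onset time. This is detail that an analyst can supply from the rules already there: count the AE unless available information shows that it began before the first dose. Carried-over AEs are settled by SAP 5.3.1 and SAP 5.5.1.

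The possible effect is 4.0 points per affected subject at N = 25, for a subject with no other TEAE. The documents give no rate of missing dates or times, so it may be zero. SAP 1.1 states that no adverse events were reported; the remark explains why no flag for AEs of special interest was derived, but read literally it makes the realised effect nil. SAP 2 makes the study descriptive, so no test depends on the classification, and all AEs are listed, so a reader could see a doubtful one. The conclusion assumes that carried-over AEs can be identified in the database, as SAP 5.5.1 presupposes, and that the routine date queries of Protocol 13.2 are made.

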6.6 Appendix 6: Data Transferred from Study INDV-6000-403

Some data will be transferred from the INDV-6000-403 study database to serve as the screening visit results, as these data are not being re-collected in this extension study (see **Table 3**).

- Demographic data (age, age category, sex, race ethnicity, child-bearing potential, and height) will be transferred from the screening visit of the INDV-6000-403 database.
 Weight, and BMI will be transferred from the EOT visit of the INDV-6000-403 database. Together, these data will serve as the demographic data at the screening visit for this study.
- Medical/psychiatric history and substance use history (tobacco use, caffeine use, drug
 use history) will be transferred from the screening visit of the INDV-6000-403
 database to serve as the data for the screening visit of this study. The
 medical/psychiatric history conditions will be coded using the process and MedDRA
 version per the study coding guidelines.
- The EOT urine pregnancy test result (from the eCRF entry) will be transferred from the INDV-6000-403 database to serve as the screening visit result for this study.
- The EOT UDS test results (from the eCRF entry) will be transferred from the INDV-6000-403 database to serve as the screening visit results for this study.

6.7 Appendix 7: Demographic and Baseline Characteristics

The demographic and disease characteristics at screening (age, age category, sex, race, ethnicity, weight, height, BMI, BMI category, tobacco use, caffeine use) will be summarised for the safety population using descriptive statistics.

The number and percentage of subjects reporting medical/psychiatric history events will be tabulated by SOC and PT, by decreasing frequency, using observed data.

